7.4 Appropriateness of Measurements

The criteria for assessing the safety and efficacy of *Wilate* in the prevention and treatment of BEs as well as in surgical prophylaxis are identical to those used in a similar study with *Wilate* in patients aged ≥ 12 years, i.e., WIL-27. The measurements of the essential tolerability and immunogenicity parameters assessed in this study are also identical to those used in WIL-27. Inhibitor measurements are performed by a central laboratory using validated assays.

Version 02

19-Jun-2017

8 DATA HANDLING AND RECORD KEEPING

8.1 Documentation of Data

8.1.1 Source Data and Records

Source data are defined as all information related to clinical findings, observations, or other activities in the study, written down in original records or certified copies of original records, allowing reconstruction and evaluation of the clinical study.

The Investigator will maintain adequate source records (e.g., case histories or patient files for each patient enrolled). Source records should be preserved for the maximum period of time required by local regulations.

For each patient enrolled, the Investigator will indicate in the source record(s) that the patient participates in this study.

All data entered in the eCRF must be supported by source data in the patient records.

The Investigator will permit study-related monitoring, audits, IEC/IRB reviews, and regulatory inspections, by providing direct access to the source data/records.

The Investigator may authorize site staff (e.g., sub-investigators, nurses) to enter study data into the eCRF. This must be documented in the Delegation of Authority Log signed by the Investigator.

8.1.2 Case Report Forms

For each patient enrolled, an electronic CRF (eCRF) will be completed within the Electronic Data Capture (EDC) system and approved by the Investigator or an authorized sub-investigator.

Study site staff (e.g., research nurse) will be responsible for entering patient data into the validated EDC system. All site personnel will be trained on the EDC system and study-specific eCRFs prior to receiving access to the live database for data entry.

The site is also provided with the approved eCRF Completion Guidelines which will assist in data entry and data issues/questions. The site will be notified once the database is active to begin data entry. Additional site training may be provided as refreshers throughout the study, if needed. All persons allowed to enter or change eCRF data must be listed in the Delegation of Authority Log.

8.1.3 Changes to Case Report Form (CRF) Data

Monitors will perform source data verification (SDV) as defined for the study.

If any errors or discrepancies in the eCRFs are found during data entry or review, discrepancies will be generated programmatically within the EDC system, and 'manual' queries will be generated by either a monitor or Data Management.

Discrepancies and queries can only be corrected by the Investigator(s) or other authorized site personnel. An audit trail documents all changes to the data over the entire study period. If the reason for a change is not obvious, a comment must be supplied in the query's response, stating the reason for the change, prior to closing. The study monitor should provide guidance to Investigator(s) and the Investigator(s)' designated representatives on making such corrections.

Once queries have been resolved by the site staff, the resolutions are assessed by Data Management. If the query response provided confirms the data as correct, the discrepancy will be closed. If the response does not adequately address the question raised, a new query will be issued for further clarification.

Manual checks are performed and programs are run throughout the study until the data is clean and the database is ready for lock. All discrepancies will be resolved prior to database lock. There will be a final run of the programmed checks to ensure all discrepancies are closed out, SDV will be confirmed as complete by the monitor, and all eCRFs will be approved by the Investigator prior to database lock.

8.2 Information to Investigators

An Investigator's Brochure (IB) will be handed out to the Investigator before the start of the study. The IB contains all information in the Sponsor's possession necessary for the Investigator to be fully and accurately informed about the safety of the IMP under evaluation and the respective benefit-risk ratio.

The IB will be updated by the Sponsor at regular intervals and whenever relevant new information concerning the IMP becomes available.

The Investigator will be informed about the methods for rating relevant study outcomes and for completing eCRFs to reduce discrepancies between participating Investigator and study sites.

The Investigator will be kept informed of important data that relate to the safe use of the IMP as the study proceeds.

8.3 Responsibilities

The Principal Investigator is accountable for the conduct of the clinical study. Responsibilities may be delegated to appropriately qualified persons.

A Delegation of Authority Log will be filled in and signed by the Principal Investigator. In accordance with this authority log, study site staff (e.g., sub-investigators, nurses) is authorized to perform tasks relating to the study.

8.4 Investigator's Site File

At each study site, the Investigator is responsible for maintaining all records to enable the conduct of the study to be fully documented. Essential documents as required by GCP guidelines and regulations (e.g., copies of the protocol, study approval letters, all original informed consent and assent forms, drug dispensing and accountability logs, correspondence pertaining to the study, etc.) should be filed accurately and kept by the Investigator for the maximum period of time required by local regulations.

The Investigator is responsible for maintaining a confidential patient identification code list, which provides the unique link between named source records and CRF data for the Sponsor. The Investigator must arrange for the retention of this confidential list for the maximum period of time required by local regulations.

No study document should be destroyed without prior written agreement between the Investigator and the Sponsor. Should the Investigator elect to assign the study documents to another party, or move them to another location, the Sponsor must be notified in writing.

8.5 Provision of Additional Information

On request, the Investigator will supply the Sponsor with additional data relating to the study, or copies of relevant source records, ensuring that the patient's confidentiality is maintained. This is particularly important when CRFs are illegible or when errors in data transcription are encountered. In case of particular issues or governmental queries, it is also necessary to have access to the complete study records, provided that the patient's confidentiality is protected in accordance with applicable regulations.

9 STATISTICAL METHODS AND SAMPLE SIZE

The statistical analysis will be delegated under an agreement of transfer of responsibilities to an external CRO that agrees to meet all Octapharma procedures and policies.

9.1 Determination of Sample Size

The sample size of 10 pediatric patients to be enrolled was based on medical and regulatory reasoning. No statistical sample size estimation was performed.

9.2 Statistical Analysis

The primary approach to the statistical analysis will be descriptive, presenting sampling statistics (n, mean, standard deviation, quartiles and range) for continuous measurements and absolute and relative frequency counts for categorical/ordinal data. This will be complemented by the presentation of exploratory confidence intervals (CIs) for means or proportions.

A formal Statistical Analysis Plan (SAP) describing all details of the analyses to be performed will be prepared by the study statistician and approved by the Sponsor prior to the start of the statistical analysis.

9.2.1 Populations for Analysis

The safety (SAF) set will include all patients who received at least one infusion of IMP.

The **full analysis set (FAS)** defined according to the intention-to-treat (ITT) principle will include all enrolled patients who received at least one infusion of IMP after the initial PK Visit.

The **pharmacokinetic** (**PK**) set will include all patients for whom a valid *Wilate* PK profile has been obtained.

The **per-protocol (PP) set**, i.e., a subset of the FAS, will exclude patients with major protocol deviations which may have an impact on the evaluation of the efficacy outcome parameters. Examples of major and minor protocol deviations will be described in the SAP.

The **surgery (SURG) set** will be a subset of the FAS, containing all patients who underwent a surgical procedure treated with *Wilate* during their Prophylactic Treatment Phase.

A final decision about the classification of protocol deviations and their consequences regarding assignment of patients to analysis sets will be made during the data review meeting. Decisions and outcome will be approved by the Sponsor.

- The analysis of safety will be based on the SAF set.
- Analysis of the PK properties of *Wilate* will be based on the PK set.
- The evaluation of the primary efficacy endpoint will be performed on the FAS (ITT analysis) and on the PP set (PP analysis).
- For secondary endpoints, ITT and additionally PP analyses will be carried out unless these analysis sets are identical.
- Analysis of the efficacy and safety of *Wilate* in surgeries will be based on the SURG set.

9.2.2 PK and Efficacy Analysis Plan

Pharmacokinetic Analysis

The analysis of the pharmacokinetic profiles of Wilate will be based on the FAS and the PP set.

The following PK parameters for FVIII:C will be analysed both for the chromogenic (CHR) and one-stage (OS) assays and actual IMP potencies:

- Area under the curve (AUC) and AUC normalized for the administered dose (AUC_{norm})
- In vivo half-life $(T_{1/2})$
- Maximum plasma concentration (C_{max})
- Time to reach maximum plasma concentration (T_{max})
- Mean residence time (MRT)
- Volume of distribution (Vd)
- Clearance (CL)
- Incremental in vivo recovery (IVR)

FVIII:C will be measured in the vials used for PK injections as well as in plasma using the CHR and OS assays.

- AUC of Wilate will be calculated from FVIII:C plasma levels measured at predefined time points and normalized for the administered dose (AUC_{norm}) using actual IMP potencies.
- All other PK parameters will be calculated from FVIII:C plasma levels measured at predefined time points using actual IMP potencies.
- Incremental IVR will be calculated from FVIII:C plasma levels measured before injection and peak levels obtained in the 15-min post-injection sample using actual IMP potencies.

The PK profiles of *Wilate* and the PK parameters derived from them will be summarized by descriptive statistics as well as the presentation of concentration vs. time plots.

For all patients, the results of the IVR assessments over time will also be analyzed in summary tables for each time point and their differences to baseline along with 95% CIs for the mean differences.

Analysis of variance (ANOVA) will be used in an exploratory sense to assess a possible association between AB0 blood type, VWF:Ag, and the FVIII:C half-life of *Wilate*.

Efficacy of Prophylactic Treatment with Wilate

Primarily, all obtained data on treatment characteristics (IMP dosages, frequencies, total consumption) and BEs (duration, frequency, efficacy assessment) will be described by providing summary statistics.

The efficacy of prophylactic treatment with *Wilate* will be statistically evaluated by presenting descriptive sampling statistics for the TABR and SABR, along with an exploratory 95% CI for the mean.

Efficacy in the Treatment of Breakthrough BEs

To assess the hemostatic efficacy of *Wilate* in the treatment of breakthrough bleedings, a frequency distribution of all such BEs being successfully treated will be presented, along with an exploratory 95% CI.

Analysis of Other Secondary Endpoints

The statistical analysis of other secondary endpoints will be descriptive, including exploratory 95% CIs for the location parameters.

Subgroup Analyses

The analyses of the PK parameters and the efficacy endpoints 'efficacy of prophylactic treatment' and 'efficacy in treatment of breakthrough BEs' will be presented for the following subgroups:

- Age '1 to <6 years'
- Age '6 to <12 years'

9.2.3 Safety Analysis Plan

All safety analyses will be based on the SAF population.

The analysis of safety will be based on the occurrence of AEs, the results of the safety laboratory tests, immunogenicity measurements, and the occurrence of parvovirus B19 seroconversions.

AEs will be coded according to the latest Medical Dictionary for Regulatory Activities (MedDRA) version. The analysis will include only treatment-emergent adverse events (TEAEs), i.e., AEs that started or worsened after the start of IMP infusion. All TEAEs, related TEAEs (i.e., TEAEs probably or possibly related to the IMP), and serious TEAEs will be summarized and tabulated according to MedDRA primary system organ class and preferred term.

Patient listings will be provided for patients with SAEs, AEs leading to withdrawal from study, and AEs leading to death.

Time profiles of the safety laboratory parameters will be analyzed by presenting sampling statistics for the values as well as their difference to baseline at each time point. Additionally, frequency tables for values outside the normal ranges will be presented.

Similarly, time profiles of FVIII inhibitor testing results will be analyzed by presenting sampling statistics for the values as well as frequency tables for positive findings, along with 95% Pearson-Clopper CIs.

To assess the viral safety of *Wilate*, incidences of parvovirus B19 seroconversions between screening and end of study will be estimated along with 95% Pearson-Clopper CIs.

Other safety parameters (e.g., changes in physical examination findings) will be analyzed by summary tables or listings.

The analysis of the safety parameters recorded during surgery (lab values) will be purely descriptive and presented as summary tables or listings.

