6.1.1 Screening Visit

The following assessments will be performed during the Screening Visit:

- Obtaining voluntarily given, written (signed and dated) informed consent
- Inclusion and exclusion criteria
- Demographic characteristics
- Weight
- Height
- Medical history (including FVIII treatment during the last 6 months before screening)
- Vital signs
- Physical examination
- Hemophilia Joint Health Score (HJHS), unless obtained within 3 months before the Screening Visit
- Blood sampling for the following purposes:
 - Routine safety laboratory
 - Determination of CD4+ levels
 - Determination of AB0 blood group (unless derived from medical history)
 - Determination of FVIII inhibitors
 - Testing for parvovirus B19 antibodies
 - Retention sample for possible additional virus marker testing
- Concomitant medications

The interval between the Screening Visit and the PK Visit should not exceed 30 days. If the 30-day interval is exceeded, determination of the CD4+ count is to be repeated and must be $>200/\mu$ L for patients to be enrolled (i.e., inclusion criterion no. 4, see Section 4.1.2).

Any BEs occurring between the Screening Visit and the PK Visit should be treated with the patient's previously used FVIII concentrate. Similarly, prophylactic treatment between the Screening Visit and the PK Visit should be done with the patient's previously used FVIII concentrate.

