7.3.5.1 Central Laboratory

The following laboratory tests will be done at the central laboratory:

- **FVIII:**C in the vials used for PK injections as well as in plasma using the CHR and OS assays
- **FVIII inhibitor activity** will be determined at each study visit before the injection of *Wilate* using the modified Bethesda assay (Nijmegen modification). Blood sampling for inhibitor testing should preferably be performed at the time of trough FVIII:C levels.

If inhibitor development is suspected between study visits (e.g., based on an unexplained need to increase the dose, lack of efficacy of IMP injections, or prolonged bleeding) (see also **Section 6.1.8**), additional FVIII inhibitor tests will be performed and documented.

In case of positive inhibitor results, inhibitor retesting using a second, separately drawn sample should be performed, preferably within 15 days of becoming aware of the positive result. If inhibitor development is confirmed by the second sample analyzed in the central laboratory, patients with low-titer inhibitors (<5 BU) may continue treatment with *Wilate*, while patients with high-titer inhibitors will be discontinued from the study.

- VWF:Ag and VWF:Ac will be measured at prespecified time points.
 - **VWF:Ac** will be measured by INNOVANCE® VWF Ac (Siemens Healthcare Diagnostics), which is a particle enhanced assay for the automated determination of VWF activity in human citrated plasma. The assay principle makes use of the binding of VWF to its receptor Glycoprotein Ib (GPIb). GPIb is the main VWF receptor on platelets. Polystyrene particles are coated with an antibody against GPIb. Recombinant GPIb (two gain-of-function mutations included) is added and binds to the antibody as well as to the VWF of the sample. Due to the gain-of-function mutations, VWF binding to GPIb does not require ristocetin. This VWF binding induces a particle agglutination which can be measured as an increase in extinction by turbidimetric measurements.
- **Virus safety** will be evaluated by taking a plasma sample for parvovirus B19 antibody testing during the Screening Visit. All patients negative during screening will be tested again at the Study Completion Visit.
 - A retention serum sample for possible virus marker testing will be taken during the Screening Visit and stored at the central laboratory.

Central laboratory:

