2.4 Study design

This study is designed as a prospective, non-controlled, international, multi-center phase 3 study. Further details are given in the overview below:

FLOW CHART FOR PK ASSESSMENT AND PROPHYLACTIC TREATMENT

| | Screening Visit | PK Visit | Prophylactic Treatment Phase (starts with first prophylactic injection of Wilate after the PK Visit) | | | | Follow-up Contact 30 (±3) days after Study Completion Visit |
|---|-----------------|----------|--|------------------------|--------------------------|---|---|
| | | | Day-14 Visit (14–21 days) | Day-30 Visit (±3 days) | 3-Month Visit (±2 weeks) | Study Completion (6-Month) Visit at 6 months (+2 weeks) | |
| Informed consent | x | | | | | | |
| Inclusion and exclusion criteria | x | | | | | | |
| Demographics | x | | | | | | |
| Weight | x | x [1] | | | x [1] | x [1] | |
| Height | x | | | | | | |
| Medical history (incl. FVIII treatment 6 months before screening) | x | | | | | | |
| Vital signs | x | x [2] | | | x [4] | x [4] | |
| Physical examination | x | | | | | x | |
| Routine safety laboratory | x | x [3] | | | x [1] | x [4] | |
| Determination of CD4+ levels [8] | x | | | | | | |
| Determination of AB0 blood group [9] | x | | | | | | |
| HJHS, unless obtained within 3 months before screening | x | | | | | | |
| PK injection (50 ± 5 IU/kg) | | x | | | | | |
| Blood sampling for FVIII:C (OS and CHR) for PK assessment | | x [5] | | | | | |
| IVR injection | | | | | x | x | |
| Blood sampling for FVIII:C IVR (OS and CHR) | | | | | x [6] | x [6] | |
| Factor VIII inhibitor [10] | x | x [1] | x [1] | x [1] | x [1] | x [1] | |
| VWF:Ag and VWF:Ac | | x [6] | x [1] | x [1] | x [6] | x [6] | |
| Parvovirus B19 antibodies | | x [1] | | | | x [7] | |
| Retention sample for possible virus marker testing | | x [1] | | | | | |
| Patient diary review | | | x | x | x | x | |
| Adverse event monitoring | | x | » | » | » | x | x [11] |
| Concomitant medications | x | » | » | » | » | x | |

PK = pharmacokinetic, IVR = in vivo recovery, HJHS = Hemophilia Joint Health Score, OS = one-stage assay, CHR = chromogenic assay, VWF:Ag = von Willebrand factor antigen, VWF:Ac = VWF activity

STATISTICAL ANALYSIS PLAN

Protocol No: WIL-30

Version Number: 1.2

Date of Issue: 2019-07-08

Page 12 of 27

LEGEND TO THE FLOW CHART FOR PK ASSESSMENT AND PROPHYLACTIC TREATMENT

- [1] Before injection
- [2] Before injection as well as 1 h (± 5 min) and 48 ± 2 h after injection

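### Protocol v02 counts parvovirus B19 seroconversions from Screening, before any Wilate is given; SAP v1.2 counts from the PK Visit, and the two must be reconciled

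*Protocol*

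**What the plan says.** Protocol v02:

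- Section 7.3.5.1 takes a plasma "sample for parvovirus B19 antibody testing during the Screening Visit". It adds: "All patients negative during screening will be tested again at the Study Completion Visit". Section 6.1.2 (PK Visit) lists neither a B19 nor a retention sample, and the Protocol flow chart agrees.
- Section 6.1.1: "prophylactic treatment between the Screening Visit and the PK Visit should be done with the patient's previously used FVIII concentrate". Bleeds in that period are treated with the same product. On timing: "The interval between the Screening Visit and the PK Visit should not exceed 30 days". The consequence of a longer gap is limited to one test: "If the 30-day interval is exceeded, determination of the CD4+ count is to be repeated".
- Section 9.2.3: "incidences of parvovirus B19 seroconversions between screening and end of study will be estimated along with 95% Pearson-Clopper CIs". The sentence presents this as the assessment of Wilate's viral safety, which is secondary endpoint 10 in section 3.1.2.
- Section 7.3.5.1 on the stored serum: "A retention serum sample for possible virus marker testing will be taken during the Screening Visit and stored at the central laboratory".

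SAP v1.2:

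- The flow chart in section 2.4 marks both the B19 antibody test and the retention sample at the PK Visit, before injection. The Screening cells are empty.
- Section 5.1.1 defines baseline as the PK Visit, with Screening used only for assessments not scheduled at the PK Visit.
- Section 5.2.1 tabulates B19 antibody results at the PK Visit, and section 5.10.3 counts seroconversions from baseline to end of study.
- Section 3.2 states that no deviations from the protocol are planned.

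**The concern.** Under the Protocol, the interval used to judge Wilate begins before the child has received any Wilate. A child who is B19-negative at Screening may acquire the virus in the community, or from the earlier concentrate if that product is plasma-derived. Inclusion criterion 3 does not restrict the type of concentrate, and section 1.1 recognises both plasma-derived and recombinant products. Such a child tests positive at the Study Completion Visit and enters the numerator. There is no sample in between to show that the conversion came first.

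The Protocol is stricter for adverse events: section 9.2.3 analyses only those that began or worsened after the start of infusion. Section 1.5 concedes that the virus measures may be of limited value against B19, so this is the agent for which a clean starting point matters most. With 10 children enrolled, and only the seronegative ones at risk, a single conversion shapes the result.

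The SAP adds a second problem. Its B19 table and its baseline presuppose a PK-Visit sample that the Protocol does not ask sites to draw.

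**Working it through.** The documents give no B19 rate, expected count or number of seronegative children, and no statistical sample size estimation was performed. There is therefore no figure of theirs to reproduce.

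**Step 1: the two schedules.**

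| Item | Protocol v02 | SAP v1.2 |
|---|---|---|
| First B19 sample | Screening | PK Visit, pre-injection |
| Retention serum | Screening | PK Visit, pre-injection |
| Start of B19 count | Screening | Baseline (PK Visit if scheduled there) |
| Baseline B19 table | not specified | PK Visit |
| First Wilate dose | PK Visit | PK Visit |

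If sites sample as the Protocol says, the SAP's PK-Visit table has no data. The only available starting value is the Screening result, so the count falls back to Screening.

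**Step 2: share of the interval before any Wilate.** Let w be the Screening-to-PK gap in days. The PK phase lasts 2 days (section 5.4.1), and the Study Completion Visit falls 6 months (about 183 days), or up to 2 weeks later (197 days), after prophylaxis starts. I assume that prophylaxis starts directly after the PK phase. Share = w / (w + 2 + 183), or w / (w + 2 + 197) at the end of the window.

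- w = 30 (the Protocol's soft limit): 30/215 = 14%; 30/229 = 13%.
- w = 14 (assumed): 14/199 = 7%; 14/213 = 7%.
- w = 60 (assumed): 60/245 = 24%; 60/259 = 23%.

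With the first sample taken before the PK injection, the share is essentially zero.

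**Step 3: effect of one misattributed conversion.** These are exact Clopper-Pearson 95% intervals. The number seronegative is an assumption, bounded above by the 10 enrolled.

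- 5 seronegative: 0/5 gives 0 to 52.2%; 1/5 gives 0.5 to 71.6%.
- 10 seronegative: 0/10 gives 0 to 30.8%; 1/10 gives 0.3 to 44.5%.

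**Step 4: how likely that is.** Assume a constant rate r of 2 to 20% per year and n = 5 to 10 seronegative children. The chance of at least one conversion in d days is 1 − exp(−r·n·d/365.25).

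- 30-day gap: from 1 − exp(−0.02·5·30/365.25) = 0.8% to 1 − exp(−0.20·10·30/365.25) = 15%.
- Wilate period of 185 days: from 1 − exp(−0.02·5·185/365.25) = 5% to 1 − exp(−0.20·10·185/365.25) = 64%.

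At any constant rate, most background conversions would occur during Wilate treatment, and moving the sample does not remove those.

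**The case against.** The case against acting has several parts.

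- **The SAP already has it right.** Under the SAP's schedule the problem does not arise. That is true of the SAP read alone, but sites draw blood by the Protocol, and the SAP cannot use a sample that was never taken.
- **Versions.** Protocol v02 is for Ukraine only. The SAP v1.2 title page also names Protocol v03, which is not among the documents, while SAP section 1 lists Protocol Version 1.0 as the material considered. The SAP flow chart includes a 9-hour PK sample that Protocol v02 lacks, so the chart may be inherited from another protocol version. This stands: the SAP chart is weak authority for what was intended. The contradiction with v02 remains.
- **Direction and size.** The extra time can add conversions to Wilate's count but cannot hide one, so the error is conservative for a safety endpoint in an uncontrolled, descriptive study. At a 30-day gap, 185 of 215 days (86%) are on Wilate anyway. This stands and limits the point to a minor one.
- **Case-by-case reading.** Prior FVIII treatment and concomitant medication are recorded, and all data are listed by subject, so each converter can be described. Section 7.3.3 requires virus antigen, not passively transferred antibody alone, before a transmission is suspected. This lessens the harm, but the reported incidence and its interval would still include pre-Wilate time.

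A reader might also infer that the retention serum biases the result. The documents do not support that: it is kept for possible testing and enters no planned analysis. Drawn at Screening, it still predates all Wilate and is only a less clean reference.

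**Conclusion.** The point holds as a contradiction between Protocol v02 and SAP v1.2 with a small, avoidable bias. If the Protocol schedule is followed, about 14% of the B19 interval for a 30-day gap comes before any Wilate exposure (7% for 14 days, 24% for 60 days, both assumed). A conversion in that time is attributed to Wilate, and the SAP's PK-Visit B19 table cannot be produced as labelled.

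The shares rest on the visit schedule and on prophylaxis starting directly after the PK phase. The conversion probabilities rest on assumed background rates and assumed numbers of seronegative children.

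Three stronger readings are not supported:

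- That the gap dominates non-Wilate exposure: community exposure over six months of treatment is larger and remains after the fix.
- That a known number of infusions of the earlier product falls in the gap: the documents do not fix the prior regimen, and the product may be recombinant.
- That the 30-day limit will in fact be exceeded: the Protocol allows for it but gives no expected frequency.

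**What to change.** 1. Bring Protocol sections 6.1.1, 6.1.2, 7.3.5.1 and 9.2.3 and the Protocol flow chart into line with the SAP. The B19 antibody sample, and preferably the retention serum, would be drawn before the PK injection.
2. State the same starting point in Protocol 9.2.3 and SAP 5.10.3: seroconversions counted from that pre-injection sample to end of study, with the children B19-negative at that sample as the denominator.
3. Correct the protocol version listed in SAP section 1, so that it is clear which schedule the SAP flow chart follows.
4. For any child with only a Screening sample, relabel the SAP 5.2.1 entry accordingly. For each converter, report the Screening-to-PK gap and the prior FVIII product, and state that the incidence includes pre-Wilate time. Stored pre-dose plasma should be tested only if residual volume and consent allow; the documents do not show that any remains.

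The cost is small. Blood is already drawn before the PK injection, so the pre-dose volume rises slightly, which matters in small children but is offset at Screening. A protocol amendment with the submissions described in section 10.4 is needed. SAP v1.2 was issued after the database review meeting, so if sampling is already complete, only items 2 (with the available first sample as the stated start), 3 and 4 can still be applied.
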